7.2.5 Sponsor Responsibility for Reporting Adverse Events

All Adverse Events will be reported to regulatory authorities, IRB/IECs and investigators in accordance with all applicable global laws and regulations.

7.3 TRIAL GOVERNANCE AND OVERSIGHT

7.3.1 Data Monitoring Committee

To supplement the routine monitoring outlined in this protocol, a separate Standing Internal Data Monitoring Committee (siDMC) will monitor the interim data from this trial. The siDMC comprises members of Sponsor Senior Management, none of whom are directly associated with the conduct of this trial. The siDMC will monitor the trial at an appropriate frequency (see Section 8.2.9 - Interim Analyses) for evidence of adverse effects of trial treatment and efficacy targets/dose selection/futility, as described in the detailed monitoring guidelines. The siDMC will determine whether the trial should continue (or other modifications, pre-specified or otherwise, should be made) according to the protocol, considering the overall risk and benefit to trial participants. The siDMC will also make recommendations to the Sponsor protocol team regarding steps to ensure both subject safety and the continued ethical integrity of the trial.

Specific details regarding responsibilities of the siDMC will be described in a separate charter that is reviewed and approved by the siDMC.

8.0 STATISTICAL ANALYSIS PLAN

8.1 Statistical Analysis Plan Summary

This section contains a brief summary of the statistical analyses for this trial. Full detail is in the Statistical Analysis Plan (SAP) (Section 8.2).

8.1.1 Parts 1 and 2: Pembrolizumab in Combination with Trametinib and Dabrafenib

The primary purpose of Part 1 and Part 2 is to investigate the safety and tolerability of pembrolizumab in combination with trametinib and dabrafenib in adult subjects with advanced melanoma. Descriptive tables that summarize the number and percentage of subjects who experience a DLT (dose limiting toxicity) as well as AE summaries will be generated for MK+D+T (as well as for MK+D, if MK+D combination is studied) by dose level for the all subjects as treated population. Percentage of subjects treated with the confirmed dose of (MK+D+T) (across Parts 1 and 2) that attained Objective Response will be estimated.

The final number of subjects enrolled in Part 1 and Part 2 of (MK+D+T) will depend on empirical safety (DLT) observations. The sample size of Part 1 will range from 3 (0/3 DLTs on Dose Level 1) to 12 subjects (6 subjects on Dose Level 1 followed by de-escalation and enrollment of 6 subjects into Dose Level -1); a likely size of 6 subjects is used as an

estimated size of Part 1 for operation purposes. If the safety of MK+D+T Dose Level 1 is acceptable, the sample size of Part 2 will range from 8 (if 6 subjects enrolled in Dose Level 1 in Part 1 are followed by enrollment of 8 more patients in Dose Level 1 in Part 2) to 24 subjects (if 3 subjects enrolled in Dose Level 1 in Part 1 are followed by enrollment of 10 more subjects in Dose Level 1 in Part 2 with 5/13 DLTs, followed by de-escalation and enrollment of 14 subjects on Dose Level -1); 11 subjects is used as an estimated size of Part 2 for operational purposes.

However, the most likely scenario is that after the MAD is identified in dose escalation (Part1), the enrollment will continue on that dose in Part 2 until 14 subjects across Parts 1 and 2 are enrolled on that dose. Thus, the most likely scenarios will include 14 subjects enrolled across Parts 1 and 2 combined (used for operational purposes), with the range across Parts 1 and 2 being 14 to 27.

8.1.2 Parts 1, 2, 4, and 5: Pembrolizumab in Combination With Trametinib

The safety and tolerability of (MK+T) (Table 3) in adult subjects with advanced melanoma will be investigated in dose escalation (Part 1) and dose confirmation (TPI design of Part 2) of the study.

The final number of subjects enrolled in Part 1 and Part 2 of (MK+T) will depend on empirical safety (DLT) observations. The sample size of Part 1 will range from 3 (0/3 DLTs at Dose Level 1) to 12 subjects (6 subjects at Dose Level 1 followed by de-escalation and enrollment of 6 subjects at Dose Level -1); a likely size of 6 subjects is used as an estimated size of Part 1 for operation purposes. If the safety of (MK+T) Dose Level 1 is acceptable, the sample size of Part 2 will range from 34 (if 6 subjects enrolled at Dose Level 1 in Part 1 are followed by enrollment of 34 more patients at Dose Level 1 in Part 2) to 50 subjects (if 3 subjects enrolled at Dose Level 1 in Part 1 are followed by enrollment of 10 more subjects at Dose Level 1 in Part 2 with 5/13 DLTs, followed by de-escalation and enrollment of 40 subjects at Dose Level -1); 34 subjects is used as an estimated size of Part 2 for operational purposes.

The safety and tolerability of the concurrent (Table 6) and intermittent (Table 7) dosing regimens of (MK+T) in adult subjects with melanoma or solid tumors will be investigated in dose escalation (Part 4) and dose confirmation (modified TPI design of Part 5) of the study. After 14 subjects are observed for DLTs on the (MK+T) dose of the concurrent regimen confirmed in Part 4 of the study and 14 subjects are observed for DLTs on the (MK+T) dose of the intermittent regimen confirmed in Part 4 of the study (across the dose escalation and confirmation parts combined), the choice of the regimen (concurrent or intermittent) for the efficacy expansion will be complete.

The final numbers of subjects enrolled in Parts 4 and 5 will depend on empirical safety (DLT) observations for both regimens. For operational purposes, the sample sizes of Parts 4 and 5 are estimated as follows.

The minimum size of Part 4 for the concurrent dosing cohort is 6 subjects which can occur if the first dose is rejected with 3 subjects and the dose below it is rejected with 3 subjects. Assuming 6 subjects per dose in the 3+3 design, the maximum size of Part 4 for the concurrent dosing cohort is 24 subjects. The minimum size of Part 5 TPI (dose confirmation) is then 8 subjects; the estimated sample size of the Part 5 TPI is increased to 16 subjects to allow for dose escalation and de-escalation steps, in the event this becomes necessary. Thus, for operational purposes, the maximum estimated subject numbers for enrollment in the concurrent dosing cohort in Parts 4 and 5 are 24 and 16, respectively, for a total of 40 subjects across Parts 4 and 5.

Similarly, the minimum size of Part 4 for the intermittent dosing cohort is 6 subjects, which can occur if the first dose is rejected with 3 subjects and the dose below it is rejected with 3 subjects. Assuming 6 subjects per dose in the 3+3 design, the maximum size of Part 4 for intermittent dosing cohort is 18 subjects. The minimum size of Part 5 TPI (dose confirmation) is then 8 subjects; the estimated sample size of the Part 5 TPI part is increased to 16 subjects to allow for dose escalation and de-escalation steps, in the event this becomes necessary. Thus, for operational purposes, the maximum estimated subject numbers for enrollment in the intermittent dosing cohort in Parts 4 and 5 are 18 and 16, respectively, for a total of 34 subjects across Parts 4 and 5.

An efficacy evaluation of (MK+T) with respect to progression-free survival (PFS) will also be performed by Kaplan-Meier method.

8.1.3 Part 3: Pembrolizumab in Combination with Trametinib and Dabrafenib

8.1.3.1 Final Efficacy Analyses

The primary analysis population in Part 3, Intent-to-Treat Set (ITT), will include all randomized subjects. Primary endpoint in Part 3 is the Progression-Free Survival (PFS) per RECIST 1.1 defined as the time from randomization to the first documented disease progression or death due to any cause, whichever occurs first. The treatment groups will be compared in PFS by stratified log-rank test. While the randomization is stratified by ECOG PS (0 vs. 1) and LDH ($>1.1 \times \text{ULN}$ vs. $\leq 1.1 \times \text{ULN}$), due to a very low number of subjects enrolled in the stratum ECOG=1 and LDH $\leq 1.1 \times \text{ULN}$, the two strata with ECOG=1 (ECOG=1 and LDH $\leq 1.1 \times \text{ULN}$; ECOG=1 and LDH $>1.1 \times \text{ULN}$) will be combined for all analyses. A Cox proportional hazard model stratified using the same strata with Efron's method of tie handling will be used to estimate the hazard ratio and its 95% confidence interval. The Kaplan-Meier method will be used to estimate the PFS survival curve.

Secondary endpoints include objective response rate (ORR) per RECIST 1.1, response duration per RECIST 1.1, and overall survival (time to death).

The analysis strategy for primary and efficacy endpoints are provided in [Table 38](#).

Table 38 Analysis Strategy for Primary and Secondary Efficacy Endpoints in Part 3

Endpoint (Description, Time Point)	Approach [†]	Statistical Method [‡]	Analysis Population	Missing Data Approach
Progression-free-survival	P	Testing: Stratified Log-rank test Estimation: Stratified Cox model with Efron's tie handling method Kaplan-Meier method for PFS curve estimation in each treatment group	ITT	Censored at last assessment
Objective response rate	S	Stratified Miettinen and Nurminen method [100]	ITT	Subjects with missing data are considered as non-responders
Response Duration	S	Summary statistics using Kaplan-Meier method	All responders	Non-responders are excluded in analysis
Overall survival	S	Summary statistics using Kaplan-Meier method	ITT	Censored at last date
† P=Primary , S=Secondary				

8.1.3.1.1 Power of the Final Efficacy Analysis of Part 3

If the true hazard ratio is 0.5, the study will need approximately 74 PFS events to have 80% power to reject a null hypothesis of equal PFS distributions in the two groups at one-sided 0.025 Type I error. Approximately 120 subjects will be randomized in 1:1 ratio to accumulate this number of events with 0.5-year enrollment period and 2-year total study duration assuming the median PFS in the (PBO+D+T) group is 10 months (rounded up estimate of 9.4 months provided in Flaherty et al. paper [101]) and yearly dropout rate is 5%. The observed hazard ratio needs to be approximately 0.62 or lower for the treatment effect to be statistically significant. This ratio translates to approximately 6.2 months increase in median duration.

8.1.3.2 Safety Analyses of Part 3

The All-Subjects-as-Treated population will be employed for safety analyses. There will be no Tier 1 events in this study. Tier 2 and Tier 3 safety endpoints will be evaluated as described in Section 8.2.5.4.

8.1.3.3 Interim Analysis of Part 3

One interim analysis of Part 3 will be conducted to inform potential early Go/No Go decision for initiation of Phase III study before the completion of Part 3. The data from the first 80 subjects randomized into the study will be used in the interim analysis. The interim analysis

will be conducted when the first 80 subjects randomized into the study will have completed their Week 36 visit and have their central radiology assessment at Week 36 available or have discontinued prior to Week 36.

Results of the interim analysis will be reviewed by the siDMC. The endpoint(s), timing, and purpose of the interim analysis are summarized in the [Table 39](#). The decision rules and other statistical details are further described in Section 8.2.9.

Table 39 Summary of Interim Analysis Strategy

Key Endpoints for Interim Analysis	Timing of Interim Analysis	Purpose of Interim Analysis

5-category ordinal response at Week 36	First 80 randomized subjects either complete Week 36 visit or discontinue prior to Week 36 visit	
Start Phase III prior to Part 3 completionFutility

8.1.4 Subgroup Analyses

Subjects with high PD-L1 expression level are of special interest in this study. The PFS hazard estimates (95% CIs) and ORR estimates (95% CI) will be provided for the subgroups of PD-L1 positive subjects and PD-L1 negative subjects.

8.2 Statistical Analysis Plan

This section outlines the statistical analysis strategy and procedures for the study. If, after the study has begun, changes are made to primary and/or key secondary hypotheses, or the statistical methods related to those hypotheses, then the protocol will be amended (consistent with ICH Guideline E-9). Changes to exploratory or other non-confirmatory analyses made after the protocol has been finalized, along with an explanation as to when and why they occurred, will be listed in the Clinical Study Report (CSR) for the study. Post hoc exploratory analyses will be clearly identified in the CSR. No separate Statistical Analysis Plan (SAP) will be issued for this study.

8.2.1 Responsibility for Analysis/In-House Blinding

The statistical analysis of the data obtained from this study will be the responsibility of the Clinical Biostatistics department of the SPONSOR.

Parts 1, 2, 4, and 5 of this trial are conducted as open-label trials, i.e., subjects, investigators, and SPONSOR personnel will be aware of subject treatment assignments after each subject is enrolled and treatment is assigned.

The database will be locked for analysis of Parts 1 and 2 for (MK+D+T) 6 months after the enrollment of the last (MK+D+T) Part 2 subject. The database will be locked for analysis of Parts 1 and 2, 4, and 5 for (MK+T) 6 months after the enrollment of the last (MK+T) Part 5 subject. Part 3 will not be unblinded when these analyses takes place.

Part 3 of this study will be conducted as a double-blind study under in-house blinding procedures. The official, final database will not be unblinded until medical/scientific review has been performed, protocol violators have been identified, and data have been declared final and complete.

Planned interim analysis of Part 3 is described in Section 8.2.9. Blinding to Part 3 treatment assignment will be maintained at all investigational sites. The results of the interim analysis will not be shared with the investigators prior to the completion of the study. Subject-level unblinding will be restricted to an internal unblinded statistician and scientific programmer performing the interim analysis, who will have no other responsibilities associated with the study. Treatment-level results and/or subject-level data of the interim analysis will be provided by the unblinded statistician to the standing internal Data Monitoring Committee (siDMC) which consists of SPONSOR personnel. Limited additional SPONSOR personnel may be unblinded to the treatment level results of the interim analysis, if required, in order to act on the recommendations of the siDMC. The extent to which individuals are unblinded with respect to results of interim analyses will be documented by the unblinded statistician.

The processes by which recommendations and decisions are reached and communicated are documented in the siDMC charter for the SPONSOR. The protocol-specific siDMC charter will be referenced in the CSR. Prior to final study unblinding, individuals who have been unblinded at any level will not be involved in any discussions regarding modifications to the protocol, statistical methods, identification of protocol violators, or data validation efforts after the interim analyses. Key aspects of the interim analyses are described in Section 8.2.9.

The Sponsor, the investigator, and the subject will be unblinded after database lock for the final analysis of Part 3. At unblinding, the Sponsor will inform each investigator of the trial treatment allocated to subjects at their site. Subjects who are receiving treatment with pembrolizumab in combination with trametinib and dabrafenib will be allowed to continue treatment per protocol after being informed of the results of the final analysis. These subjects will continue to follow the dose modification and toxicity management guidelines as per protocol. Combinations other than the therapy they are already receiving will not be allowed for these subjects.

Subjects who are receiving treatment with placebo in combination with trametinib and dabrafenib will be allowed to continue trametinib and dabrafenib per protocol (without placebo) after being informed of the final analysis results. These subjects will continue to follow the dose modification and toxicity management guidelines as per protocol. These subjects will not be allowed to cross over to the treatment arm with pembrolizumab in combination with trametinib and dabrafenib.

8.2.2 Hypotheses/Estimation

Objectives and hypotheses of the study are stated in Section 3.0.

8.2.3 Analysis Endpoints

8.2.3.1 Efficacy Endpoints

Efficacy endpoints and their definitions are presented below.

8.2.3.1.1 Primary Endpoint

Progression-free Survival (PFS): is defined as the time from randomization in Part 3 (or the start of treatment in other Parts) to progressive disease (PD) or death, whichever occurs earlier, based upon RECIST 1.1 by the investigator review. Subjects without documented PD/death will be censored at the last disease assessment date.

8.2.3.1.2 Secondary Endpoints

Objective Response Rate (ORR): is defined as the percentage of subjects who have achieved confirmed complete response (CR) or partial response (PR) according to RECIST 1.1 by the investigator review. Subjects with missing outcome on objective response will be considered non-responders.

Response Duration: is defined as the time interval between the date of the first confirmed response (CR/PR) (the response prior to confirmation) and the date of first documented disease progression based upon RECIST 1.1 by the investigator review. Response duration will be only determined for confirmed responses.

Overall survival (OS): is defined as the time from randomization (or the start of treatment when there is no randomization) to death due to any cause. Subjects without documented death at the time of analysis will be censored at the date last known to be alive.

5-Category Ordinal Response at Week 36 – an ordinal endpoint that classifies the response at Week 36 into one of 5 categories: CR, VGPR defined as partial response with percent reduction from baseline in tumor line length >60%, MPR defined as partial response with percent reduction from baseline in tumor line length ≤60%, SD, and PD, where CR, PR, SD and PD categories are based upon RECIST 1.1 by central review. This will be the primary endpoint of the interim analysis of Part 3. See details of the definition in the description of the **5-Category Ordinal Response at a Timepoint**.

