After radiological assessment at screening, the first radiological assessment will be performed following 2 cycles of study treatment (± 7 days), unless there is clinical indication (based on Investigator's assessment) warranting earlier radiologic imaging. The same imaging technique as used at screening should be used throughout the study. After the first on-treatment imaging assessment, subjects will be evaluated every six (6) weeks up to Month 18 with radiographic imaging to assess response to treatment. Following Month 18, imaging assessment will occur every twelve (12) weeks. Investigators will make all treatment-based decisions using modified Response Evaluation Criteria in Solid Tumors (RECIST) 1.1 criteria. Imaging from Parts 1, 2, 4, and 5 for (MK+D+T) and (MK+T) and Part 3 (non-inclusive of IA) will be investigator-assessed using RECIST 1.1 for determination of endpoints (including ordinal response), but also collected and held, and may be centrally-read later by independent radiologists, retrospectively. Imaging for the first 80 patients up to Week 36 in Part 3 (subjects included in the interim analysis) will be centrally-read using RECIST 1.1 for determination of efficacy endpoints. Refer to Section 8.2.3 for additional information on endpoints. RECIST 1.1 will be adapted as described in Section 4.2.3.1 due to the tumor response patterns seen with pembrolizumab treatment (e.g., tumor flare), and this

adapted RECIST will be used by the sites for treatment decisions. Adverse events will be monitored throughout the trial and graded in severity according to the guidelines outlined in the NCI Common Terminology Criteria for Adverse Events (CTCAE) Version 4.0. In general, study treatment will continue until documented disease progression, unacceptable adverse event(s), intercurrent illness that prevents further administration of treatment, investigator's decision to withdraw the subject, subject withdraws consent, pregnancy of the subject, noncompliance with trial treatment or procedure requirements, or administrative reasons. Subjects who attain an investigator-determined confirmed complete response (CR) per RECIST after at least 6 months of pembrolizumab treatment could potentially stop trial treatment of pembrolizumab and continue treatment with trametinib and/or dabrafenib, in accordance with standard care, until disease progression or the end of study, whichever comes first.

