Percentage of Subjects with PR based upon RECIST 1.1 by the investigator review

Percentage of Subjects with Deep Response (DR) where DR is a response that is either CR or VGPR by the investigator review.

Best Target Lesion Response - maximum percent reduction in tumor line length over target lesions by the investigator review.

Time to Confirmed Response – defined only for subjects with confirmed response by the investigator review. The time interval between the date of randomization and the date of the first confirmed response (CR/PR) (the response prior to confirmation).

Percentage of Subjects with Sustained Response at Week 36 (used in the interim analysis) - subjects who achieved response (confirmed CR or PR) prior to Week 36 but have not yet progressed at Week 36 by central review.

Tumor growth kinetics endpoints: growth rate constant (GST) and time-to-growth (TTG) and other as appropriate. These endpoints will be used in Modeling and Simulations analysis.

EuroQol (EQ-5D) and EORTC (QLQ-C30) endpoints

Additional supportive analyses of PFS, objective response rate, best overall response, and duration of response will be conducted using modified RECIST 1.1 criteria, in which a confirmation assessment of disease progression must be obtained at least 4 weeks after the initial disease assessment indicating progressive disease.

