For PFS, subjects without documented PD/death will be censored at the last disease assessment date or, if they started new anti-cancer treatment, at the last disease assessment before initiation of the new anticancer treatment (Table 40). Two sensitivity analyses of PFS will be performed. The rules for defining the time of progression or censoring in the primary and two sensitivity PFS analyses are provided in Table 41.

Table 41 Censoring Rules for Primary and Sensitivity Analyses of PFS

Situation	Primary Analysis	Sensitivity Analysis 1	Sensitivity Analysis 2
No PD and no death; new anticancer treatment is not initiated	Censored at last disease assessment	Censored at last disease assessment	Censored at last disease assessment if still on study therapy; progressed at treatment discontinuation otherwise
No PD and no death; new anticancer treatment is initiated	Censored at last disease assessment before new anticancer treatment	Censored at last disease assessment before new anticancer treatment	Progressed at date of new anticancer treatment
PD or death documented after ≤ 1 missed disease assessment	Progressed at date of documented PD or death	Progressed at date of documented PD or death	Progressed at date of documented PD or death
PD or death documented after ≥ 2 missed disease assessments	Progressed at date of documented PD or death	Censored at last disease assessment prior to the ≥ 2 missed disease assessment	Progressed at date of documented PD or death

ORR will be estimated as the percentage of responders among subjects in each treatment group. 95% CIs for within-group ORRs will be provided using the Clopper-Pearson method [102]. The treatment comparison between arms will be based on Miettinen and Nurminen's method [100] based on difference in proportions stratified using strata from the PFS analysis.

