The response duration analysis will include subjects who achieved objective response. The responders who have not yet progressed by the last disease assessment will be censored at the last disease assessment date. The treatment groups will be compared in response duration by log-rank test stratified using strata from the PFS analysis. A Cox proportional hazard model with a factor for treatment group stratified using the strata from the PFS analysis with Efron's method of tie handling will be used to estimate the hazard ratio and its 95% confidence interval. The Kaplan-Meier method will be used to estimate the response duration survival curve, the 25-th percentile and the median of response duration and their 95% CIs.

Time to response analysis will include all subjects who achieved objective response, and thus, will contain no censored endpoints. The Kaplan-Meier method will be used to estimate the time to response survival curve, the 25th percentile and the median of response duration and their 95% CIs.

The treatment groups will be compared in OS by log-rank test stratified using the strata from the PFS analysis. A Cox proportional hazard model with a factor for treatment group stratified by the covariates above with Efron's method of tie handling will be used to estimate the hazard ratio and its 95% confidence interval. The Kaplan-Meier method will be used to estimate the OS survival curve, the 25th percentile and the median of OS and their 95% CIs. Subjects without documented death at the time of analysis will be censored at the date last known to be alive.

Best Overall Response (BOR) will be summarized by treatment groups, with frequency of categories presented. BOR-5 will be analyzed by ANOVA on scores 1 to 5 assigned to the response categories: CR=1, VGPR=2, MPR=3, SD=4, PD=5. ANOVA will include factors for treatment group, ECOG PS (0 vs. 1) and LDH (>1.1xULN vs. ≤1.1xULN). The variances in the two treatment groups will be allowed to be unequal. The desired effect of the addition of pembrolizumab to the (PBO+D+T) combination is to shift BOR response towards lower scores, [lower the treatment group mean score of (MK+D+T) compared to (PBO+D+T)].

Individual Best Target Lesion Responses (maximum percent reduction in tumor line length over target lesions) will be plotted for each treatment group separately in a waterfall plot.

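### Response duration ends at documented progression only, so responders who die without it are censored, and the planned curve and quantiles overstate time still in response if any such deaths occur

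*Combined protocol and SAP*

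**What the plan says.** **Response duration.** Section 8.2.3.1.2 runs the interval from the first confirmed response to "and the date of first documented disease progression based upon RECIST 1.1 by the investigator review". Death is not named. Section 8.2.5.1 gives the censoring rule: "The responders who have not yet progressed by the last disease assessment will be censored at the last disease assessment date". It then plans a stratified log-rank test, a stratified Cox hazard ratio and this estimation: "The Kaplan-Meier method will be used to estimate the response duration survival curve, the 25-th percentile and the median of response duration". In Tables 38 and 40 the missing-data entry for the endpoint deals only with non-responders.

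**PFS.** Section 8.1.3.1 ends PFS at "the first documented disease progression or death due to any cause, whichever occurs first", and Section 8.2.3.1.1 runs it "to progressive disease (PD) or death, whichever occurs earlier". Table 41 applies to PFS only. In its primary analysis, a subject with documented progression or death is "Progressed at date of documented PD or death", however many assessments were missed. Sensitivity Analysis 2 does the same. Sensitivity Analysis 1 censors the subject if two or more assessments were missed beforehand.

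**Supportive analysis.** Section 8.2.3.1.3 states: "Additional supportive analyses of PFS, objective response rate, best overall response, and duration of response will be conducted using modified RECIST 1.1 criteria". The modification concerns confirmation of progression and adds nothing about death.

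**The concern.** A responder who dies on study with no progression on record is an event in the primary PFS analysis and a censored observation in response duration. Censoring treats the response as one that could have continued after death. The Kaplan-Meier estimate then answers how long responses would last if nobody died first. Most readers of a response-duration curve want something else: the proportion of responders still alive and in response.

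This matters because Section 4.2.1 gives durability as the reason for the triplet, which is meant to join the high response rate of MAPK inhibition to the longer responses seen with pembrolizumab. Response duration is a named Part 3 secondary endpoint in Section 3.2. An unlabelled curve that removes deaths shows durability at its most favourable.

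**Working it through.** The plan states no figure for response duration, so there is nothing to reproduce. The check has a textual step and an illustration of size.

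**1. What happens to a death without progression.** The end event is documented progression (Section 8.2.3.1.2). A responder who dies without it has not progressed by the last disease assessment, so Section 8.2.5.1 censors that responder there. Tables 38 and 40 do not alter this, Table 41 is confined to PFS, and Section 8.2.3.1.3 is silent. Following the plan exactly gives one outcome: censored at the last scan.

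**2. Size under constant hazards.** Let L be the total hazard of progression or death among responders, and s the share of first events that are deaths without progression. The documents do not give s, so it is assumed. With deaths censored, Kaplan-Meier estimates exp(-L(1-s)t) instead of exp(-Lt), and every quantile is multiplied by 1/(1-s).

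| s (assumed) | 1/(1-s) | Median, if 10 months with deaths counted (assumed) | 25th percentile, if 4.15 months with deaths counted |
|---|---|---|---|
| 5% | 1.05 | 10.5 | 4.4 |
| 10% | 1.11 | 11.1 | 4.6 |
| 20% | 1.25 | 12.5 | 5.2 |

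The 4.15 months follows from the assumed 10-month median: 10 × ln(1/0.75)/ln 2.

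**3. Size when progression is dated by scan.** Section 2.1 says "subjects will be evaluated every six (6) weeks up to Month 18 with radiographic imaging". Take scans every 42 days from the response scan, or 42/(365.24/12) = 1.38 months, and ignore visit windows. The chance of a first event per interval is q = 1 - exp(-(ln 2/10) × 1.38) = 0.0912. With deaths censored at the preceding scan, the Kaplan-Meier drop at each scan is h = (1-s)q/(1-sq).

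- Deaths counted: the curve is 0.512 just after scan 7 (9.66 months) and 0.465 at scan 8 (11.04 months). Deaths between these scans leave it above 0.50 until scan 8 (0.503 even at s = 20%), so the median is 11.04.
- s = 5%: h = 0.0871, and the curve at scan 8 is 0.483. Median 11.04, no shift.
- s = 10%: h = 0.0828, with 0.501 at scan 8 and 0.459 at scan 9. Median 12.42, one interval later, but only just.
- s = 20%: h = 0.0743, with 0.539 at scan 8 and 0.499 at scan 9. Median 12.42, one interval later.

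The observed median therefore moves by nothing or by about one interval.

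**4. Between-arm hazard ratio.** The ratio is multiplied by (1 - s_triplet)/(1 - s_control). Equal shares give 0.90/0.90 = 1.00. Assumed shares of 10% versus 5% give 0.90/0.95 = 0.95, and 20% versus 10% give 0.80/0.90 = 0.89.

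**The case against.** The strongest reply is that the plan does have a rule. The censoring sentence is exhaustive, time to progression is a definable quantity, and the hazard ratio has a valid cause-specific reading. The documents never call the curve the proportion still in response. Much of this stands. A reader might infer that the plan leaves deaths undefined, but the two sections together determine the outcome. What remains is that the rule is never stated as a choice about deaths, and that the resulting curve and quantiles are unlabelled.

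A second reply is that little turns on it. The endpoint is secondary, has no multiplicity control (Section 8.2.6) and enters no decision rule. With an assumed 20 to 37 events per arm, the 95% interval for a 10-month exponential median, 10 × exp(±1.96/√events), is 6.5 to 15.5 or 7.2 to 13.8 months, wider than a 5% to 11% shift. Deaths by arm also appear in OS and among the Tier 2 safety endpoints. This limits the importance, but the shift has a known direction, and none of those outputs isolates deaths in response.

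A third reply is that the month-level figures are illustrative. That is right: s and the 10-month median are assumed. Imaging is also sparser after Month 18 (every 12 weeks) and after stopping treatment without progression (every 3 months, Section 6.3), and the ±7-day imaging window would smooth the steps.

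Finally, Section 8.2.3.1.2 ties progression to RECIST 1.1, which Section 12.4 adopts by reference only. Whether that source supports a progression-only end cannot be checked here.

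**Conclusion.** The point holds. The plan as written censors deaths without documented progression in response duration, while the primary PFS analysis and Sensitivity Analysis 2 count them. The planned curve, 25th percentile and median overstate time still in response if any responder dies without progression. The inflation is 1/(1-s) under constant hazards, with s unknown. With scan-dated progression, the median may show no shift or a shift of about one scan interval.

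Two stronger readings are not supported. A reader might infer that the hazard ratio is tilted towards the triplet, because Section 5.2.5 reports more Grade 3-5 adverse events in that arm. No count of Grade 5 events or of deaths without progression is given, so unequal shares are not shown. A reader might also infer that PFS always counts such a death, but Sensitivity Analysis 1 censors it after two or more missed assessments.

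PFS, OS and the power calculation are unaffected. The correction is worth making because it is cheap and concerns the property on which the triplet was justified.

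**What to change.** Sections 5.2.5 and 7.1.5.3 show that the Part 3 final analysis is done, so the prespecified definition should stay as it is. In the clinical study report:

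- Label the planned response-duration result as time to documented progression, with deaths without progression censored.
- Add an analysis, identified as post hoc as Section 8.2 requires, in which the event is documented progression or death from any cause, whichever is first. Censor only responders alive without progression, at the last disease assessment.
- Report, for each arm, the number of responders who died without documented progression.
- Do the same for the supportive duration analysis under modified RECIST 1.1 (Section 8.2.3.1.3).

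For Parts 1, 2, 4 and 5, Section 8.2.4.1 names a population for response duration but Section 8.2.5.1 gives no method. Use the progression-or-death definition for anything still to be reported there.

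The cost is one extra labelled analysis for each planned duration analysis and one count per arm. Death dates are already needed for PFS and OS, so no new data are required. Response duration under the added definition may be slightly shorter.
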